5.6.2.5. New Malignancy

Malignancies will be identified using data reported on the malignancy question of the eCRF (i.e. any new malignancies to report (including NMSC)). New malignancies will be assigned to Week 52, Year 2 follow-up, Year 3 follow-up, Year 4 follow-up or Year 5 follow-up based on the nominal visit of the malignancy form where a new malignancy is reported. For malignancies reported during the Week 52 double-blind treatment period, this is equivalent to PSAP defined malignancies reported in the adverse event data which occurred during the on-study period (see Section 9.1.1 of the separate Week 52 double-blind treatment period RAP).

New malignancies reported at Week 52 with a diagnosis of ‘UNKNOWN,NO FOLLOW-UP’ (SDTM.CE.CETERM) will not be considered to be malignancies.

For all malignancies, date of diagnosis will be the date of diagnosis collected on the malignancy form.

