Deaths reported during the Week 52 double-blind study period were collected as adverse event data. In the year 2-5 follow up period for BEL115467 the primary reason of death is collected on the annual FU survival form and will be coded using

the latest version of MedDRA (with SOC and PT); detailed SAE information is NOT collected. There are coding limitations for death data from the post-treatment follow-up period, as the information available to code was limited to the verbatim 'primary reason for death'.

Malignancies reported during the 52-week double-blind treatment period of the study were collected as adverse event data. New primary malignancies reported in the post-treatment follow-up period are collected on the annual FU survival form and will be coded using the latest version of MedDRA (with SOC and PT). There are coding limitations for malignancy data from the post-treatment follow-up period, as the information available to code was limited to the verbatim 'diagnosis'.

For the interim reporting efforts (Years 2, 3 and 4) every effort will be made to code all reported terms, however this may not be possible and there may be un-coded terms for interim reporting efforts.

Data for deaths and malignancies from the Week 52 double-blind treatment period adverse event data will not be re-coded as part of Years 2-5 reporting. Summary tables presenting deaths and malignancies by MedDRA SOC/PT will not include data from the Week 52 double-blind treatment period. Summaries of these data can be found in the Week 52 double blind treatment period CSR and will not be duplicated in the post-treatment follow-up summaries.

A decision was made by the Benlysta Safety Review Team (SRT) in April 2020 to stop manual categorization (using the PSAP adjudication categories described in Appendix 6 of the Week 52 double-blind treatment period RAP) of Year 2-5 deaths and malignancies for Year 3 reporting onwards for the following reasons:

- Many events cannot be definitively categorised using the limited information available from verbatim primary cause of death/malignancy diagnosis. Clinical corroboration of the reported terms is generally not possible. Ambiguities often cannot easily be resolved because it is not possible to query the site staff to follow up with the subject and/or review medical records (as was done during the treatment period of the study).

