5.6.2.8. Subject Years Follow-Up: Malignancy Subject Incidence Rate

In order to calculate the follow-up adjusted subject incidence rate of new malignancies per 100 subject years by follow-up year (cumulative), the subject years follow up will need to be defined for each subject at each follow-up time point.

This will be done in a similar way to subject years follow-up for mortality (Section 5.6.2.6) but will use date of follow-up contact, rather than date last known alive, as the censoring date. And will use date of diagnosis, rather than date of death as the event date (note: date of diagnosis using SDTM.CE.CESTDTC).

Note: New malignancies reported at Week 52 with a diagnosis of 'UNKNOWN,NO FOLLOW-UP' (SDTM.CE.CETERM) will not be considered to be malignancies (see Section 5.6.2.5).

For each subject a single date of first new malignancy or last follow-up contact date will be derived as follows.

For subjects who entered the follow-up period (i.e. are in any of the Year 2 to 5 population subsets):

- For subjects who have a new malignancy reported, the date of diagnosis of the first new malignancy will be used in the subject follow-up years calculations. Note: this includes malignancies reported by Week 52.
- For subjects who have not reported a new malignancy at any follow-up visit, the date of last follow-up contact across all follow-up visits will be found (using all visits where the new malignancy question was answered as NO) and used as the censoring date. If this follow-up contact date is later than the last known alive date (or date of death) used in the mortality subject years follow-up then the date of last known alive (or date of death) will be used as the censoring date instead.
- For subjects where the date of last follow-up contact across all follow-up visits is missing (i.e. subjects who have not reported a new malignancy and have no Year 2-5 follow-up visits where the new malignancy question was answered as NO), then the study completion or withdrawal date from the Week 52 double-blind treatment period will be used as the censoring date. In calculations, the data for these subjects will be truncated so that subject follow-up years does not exceed 365 days for these subjects.

For subjects who did not enter the follow-up period (i.e. are not in any of the Year 2 to 5 population subsets):

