7.2. Malignancy

Malignancies will be summarized by nominal follow-up visit for each treatment group and overall.

New Malignancy Percentages

The number and percentage of subjects reporting new malignancies will be summarized at each follow-up year for the categories of: new malignancy, no new malignancy and not completed. Percentages for each follow-up visit will be calculated from the number of subjects at the follow-up visit, defined as subjects included in the relevant As-Treated population subset (i.e. Year 2 follow-up, Year 3 follow-up, Year 4 follow-up, Year 5 follow-up).

The additional category 'Not completed' will be summarized for follow-up years, this includes subjects who had a non-missing survival status at this visit or a subsequent follow-up year, but did not complete the new malignancy form at this visit.

For completeness, new malignancies at the Week 52 visit will also be presented in the same table, using subjects in the As-Treated population as the denominator for percentages.

A listing of new malignancies by follow-up year will be presented, including first commercial Benlysta use.

Malignancies by System Organ Class and Preferred Term

A summary of new malignancies will be produced for each follow-up year separately (Years 2, 3, 4 and 5). For each follow-up year, the summary will include the number and percentage of subjects with new malignancies for each SOC, each PT, and overall; based on subjects in the associated year follow-up subset of the As-Treated population and malignancies reported during that follow-up year.

By default, the malignancies will be sorted by MedDRA SOCs, in descending order from the SOC with the highest total incidence (i.e., summed across all treatment groups) for any malignancies within the class, to the SOC with the lowest total incidence. If the total incidence for any two or more SOCs is equal, the events will be presented in alphabetical order. Only SOCs with observed AE PTs will be presented. Repeat sort order for MedDRA PTs within each SOC.

Cumulative Malignancies and Follow-up Adjusted Subject Incidence Rate

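### The Years 2-5 RAP never reconciles the malignancy question with the coded cause of death, so a cancer recorded only as a cause of death can drop out of the malignancy counts and rates

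*SAP*

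**What the plan says.** All references are to the Years 2-5 RAP unless stated otherwise.

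- **Event source.** Section 5.6.2.5: "Malignancies will be identified using data reported on the malignancy question of the eCRF". For Week 52, the same section equates this with PSAP-defined malignancies found in the adverse event data.
- **Cause of death.** Section 5.6: "the primary reason of death is collected on the annual FU survival form and will be coded using" MedDRA.
- **Where cancers are recorded.** Section 5.6: "New primary malignancies reported in the post-treatment follow-up period are collected on the annual FU survival form". Both items are therefore on the annual follow-up survival form.
- **Blank malignancy items.** Section 7.2 has a *Not completed* category for "subjects who had a non-missing survival status at this visit or a subsequent follow-up year, but did not complete the new malignancy form".
- **Censoring without a reported malignancy.** Section 5.6.2.8 takes the last follow-up contact, "using all visits where the new malignancy question was answered as NO". A cap applies: "If this follow-up contact date is later than the last known alive date (or date of death"), the date of death or last known alive date replaces it. If no Years 2-5 visit was answered NO, the "study completion or withdrawal date from the Week 52 double-blind treatment period will be used as the censoring date", truncated at 365 days.
- **Other sources.** Section 7 says SAEs and AESIs are not in the clinical database for these years.
- **Manual review.** Section 5.6 drops manual PSAP categorisation of deaths and malignancies from Year 3 reporting onwards.

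**The concern.** Mortality and malignancy are the only two endpoints of the four-year follow-up (Section 2.2), and contact is planned as one telephone call a year (Section 2.3). A subject can be diagnosed with cancer and die of it between two calls. The site then has a death and a short verbatim cause. Unless it also completes the malignancy item, the plan counts a cancer death but no cancer.

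Three things are at stake. The malignancy rate can read low, and the missing cases would all be fatal. The death and malignancy tables of one report can disagree with no rule to explain it. Ascertainment also changes partway through a rate that is cumulative from treatment start. In Year 1, Protocol 7.2.1 records each death as the outcome of the adverse event that led to it, so a cancer entered as that event is open to the malignancy search. In Years 2-5 the coded cause of death is not searched for malignancy.

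**Working it through.** The plan states no figure on this point, so there is none to reproduce. The check traces the rules and then illustrates their scale.

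**1. Tracing the rules.** Take a hypothetical subject whose Year 2 contact on Day 730 was answered NO. Cancer is diagnosed on Day 800, death occurs on Day 850, and the death is reported at a Year 3 contact on Day 1095.

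| Malignancy item at the death visit | Malignancy counted? | Person-time ends |
|---|---|---|
| Blank | No | Day 730, the last NO, before diagnosis |
| NO | No | min(1095, 850) = Day 850, date of death, after diagnosis |
| YES | Yes | Day 800, diagnosis |

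If a subject dies before the Year 2 contact and the item is blank, no event is counted and person-time ends no later than Day 365. In both the blank and the NO cases the death remains in the deaths by SOC and PT table and in Listing 6.

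**2. Scale, per arm.** Inputs from the documents:
- about 4,000 subjects randomised 1:1, so 2,000 per arm (Section 2.3);
- 0.45 malignancies per 100 patient-years on belimumab, excluding NMSC (Protocol 1.2).

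Assumptions, not in the documents:
- a fraction f = 60% to 100% of the possible Years 2-5 follow-up is obtained;
- a share m = 5%, 10% or 20% of malignancies is missed;
- g = 0.5 to 1 year of person-time is lost per missed case.

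Subject-years S = 2,000 + 8,000f, which is 6,800 to 10,000. Expected cases E = 0.0045 × S, which is 30.6 to 45.

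Reported rate = 100 × (E − mE) / (S − mE × g). At f = 100% and g = 0.5:
- m = 5%: 100 × 42.75 / 9,998.9 = 0.4275
- m = 10%: 100 × 40.5 / 9,997.75 = 0.4051
- m = 20%: 100 × 36 / 9,995.5 = 0.3602

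With g = 1 the results are 0.4276, 0.4052 and 0.3603. They are the same to four decimals at f = 60%. Even with four years lost per missed case, m = 20% gives 100 × 36 / (10,000 − 36) = 0.3613. The shortfall therefore comes almost entirely from the missing event. Lost person-time is negligible and slightly offsets it.

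**3. Plausibility of the assumed share.** With complete follow-up of both arms, Years 2-5 contain at most 4,000 × 4 = 16,000 subject-years. At the background SLE rate of 0.53 per 100 patient-years (Protocol 1.2), 16,000 × 0.0053 = 84.8 cases are expected, and 5% to 20% of these is 4.2 to 17.0. At the mortality rate of 0.564% used in Protocol 8.4.1, taken as annual, about 16,000 × 0.00564 = 90.2 deaths are expected. Seventeen missed cases would be 17.0 / 90.2, or about 19% of all deaths. The top of the range is hard to credit.

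**The case against.** The strongest reply is that the pathway needs a site to contradict itself. Cause of death and new malignancies are on the same annual form, no rule bars a YES for a deceased subject, and partial diagnosis dates are imputed (Section 5.6.1.1). A site that writes a new cancer as the cause of death already knows of a malignancy to report. This stands: the loss is possible, not shown.

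A reader might infer from the *Not completed* category that the RAP expects deaths with a blank malignancy item. The text does not support that. The category covers anyone with a survival response at that or a later visit who "did not complete the new malignancy form at this visit". Section 4 counts lost to follow-up and withdrew consent as responses, so the category also takes in skipped visits and uncontactable subjects. It permits the blank case without being about deaths.

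It can also be said that the cancer deaths stay visible in the SOC and PT tables and the listings, that Protocol 10.5 provides automated consistency checks in the data capture system, and that the eCRF and its edit checks are not available here. Visibility and general data checks are real mitigations. They do not put the case into a malignancy rate, however. Section 5.6 of the RAP itself says ambiguities often cannot easily be resolved, because sites cannot be asked to go back to the subject or the records.

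Finally, a verbatim cause of death cannot show that a cancer is a new primary. Exclusion criterion 6 of the protocol admits subjects whose cancer was more than five years ago, so some deaths could be recurrences. This is a sound reason not to alter the main definition, but not a reason to leave the two items unreconciled.

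**Conclusion.** The gap is real and limited. The malignancy item is the only source, nothing checks it against the coded cause of death, and a cancer recorded only as a cause of death is left out of the counts and rates. The error can only lower the reported malignancy rate, and it falls on fatal cases.

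Two stronger readings should be resisted. One is that rapidly fatal cancers are systematically lost and number 4 to 17. The documents give no share for cancers known only from the death record, so 5% to 20% is an assumption, and 16,000 subject-years assumes no loss to follow-up. The other is that such subjects are always censored before the event and that this informative censoring drives the bias. A blank item does censor early, but NO at a contact after death censors at the date of death. In either case the lost time hardly moves the rate.

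The illustrative fall from 0.45 to 0.43, 0.41 or 0.36 would show at the two decimals the RAP reports. It rests on the assumed share and on a rate that excludes NMSC, whereas the follow-up endpoint includes it. The follow-up is descriptive, with no hypothesis test (Sections 2.4 and 5.5), and nothing in the documents suggests the loss would differ by arm. The consequence is possible under-reporting and unexplained disagreement between tables, not a threat to a formal comparison.

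**What to change.** Keep the Section 5.6.2.5 definition for the main tables and add the following:

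1. A programmed cross-check that selects Years 2-5 deaths whose coded primary cause is among the malignant terms of the PSAP query. Exclude the unspecified-malignancy terms, which need clinical review. Restrict it to subjects with no malignancy recorded up to and including that visit, Week 52 included.
2. A flag for unmatched cases in Listings 6 and 7.
3. A pre-specified sensitivity version of Table 3.14 that adds the unmatched cases. Where no diagnosis date exists, use date of death as the event date and as the end of person-time.

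The RAP already does something similar. Section 5.6.2.4 identifies COVID-19 deaths by a custom MedDRA query. The cost is a paragraph of RAP text and a merge of two datasets that are already coded. At interim reports the check reaches only causes coded by then, since Section 5.6 allows for uncoded terms.

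The downside is that a few added cases may be recurrences of a pre-study cancer, or be dated later than diagnosis. For that reason they belong in the sensitivity display and not in the main count.

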5.6.2.6. Subjects Years Follow-Up: Mortality

Subject years follow-up for mortality is calculated as described below, regardless of the primary cause of death (COVID-19 or other).

In order to calculate the follow-up adjusted incidence rate of mortality per 100 subject years by follow-up year (cumulative), the subject years follow up will need to be defined for each subject at each follow-up time point.

For each subject a single date of death or last known alive date will be derived as follows.

For subjects who entered the follow-up period (i.e. are in any of the Year 2 to 5 population subsets):

- For subjects who have died, the date of death will be used in the subject follow-up years calculations.
- For subjects who have not died, the latest last known alive date across all follow-up visits will be found.

For subjects who did not enter the follow-up period (i.e. are not in any of the Year 2 to 5 population subsets):

- For subjects who have died, the date of death will be used in the subject follow-up years calculations.
- For subjects who were alive or lost to follow-up at the Week 52 survival status assessment, the last known alive date from the Week 52 survival status form will be used. In calculations, the data for these subjects will be truncated so that subject follow-up years does not exceed 365 days for these subjects.
- For subjects where the Week 52 survival status was missing, the study withdrawal or completion date (DSSTDT) will be used as the last known alive date. In calculations, the data for these subjects will be truncated so that subject follow-up years does not exceed 365 days for these subjects. Note: there were four subjects with missing Week 52 survival status where the study withdrawal or completion date was missing; for these subjects the study agent discontinuation date (IPDISCDT) was used as the last known alive date.

Using this date of death or last known alive date, the total subject follow-up will be derived for each subject as:

- Subject follow-up (days) = (Date of death/Last Known Alive Date – Study Treatment Start Date +1)

The amount of subject follow-up days contributing to each of the cumulative timepoints (by Week 52, by Year 2 follow-up, by Year 3 follow-up, by Year 4 follow-up, by Year 5 follow-up) is described below. In order to account for date of death or last known alive date which is out of the correct range of study days for a particular year, the following derivation will be used:

Study Year	Subject Follow-Up (days)
By Week 52	Minimum (Date of death/Last Known Alive Date – Treatment Start Date + 1, 365)
By Year 2 Follow-Up	Minimum (Date of death/Last Known Alive Date – Treatment Start Date + 1, 730)
By Year 3 Follow-Up	Minimum (Date of death/Last Known Alive Date – Treatment Start Date + 1, 1095)
By Year 4 Follow-Up	Minimum (Date of death/Last Known Alive Date – Treatment Start Date + 1, 1460)

Study Year	Subject Follow-Up (days)
By Year 5 Follow-Up	Minimum (Date of death/Last Known Alive Date – Treatment Start Date + 1, 1825)

Note: individual subjects will only be allowed to contribute a maximum of 365 days for each individual follow-up year, regardless of when the follow-up visit was performed.

Note: For each subject, subject follow-up for each time period is cumulative since study treatment start date. For example, 'by Year 2 follow-up' includes follow-up time during Year 1 and follow-up time during Year 2 (to a maximum of 730 days).

The subject follow-up days will be converted to years as follows:

- Subject follow-up (years) = subject follow-up (days) / 365.25

The total follow-up years will be calculated for each of the timepoints as the sum of the subject follow-up years for that timepoint for all subjects in the As-Treated population.

An example of the amount of subject follow-up days included in each year period, for subjects where the date of death or the last known alive date falls within the correct study day range for each year, is:

Subjects Enter Follow-Up Period [1]	Subject Years Follow-Up Included By Year	Subjects Years Follow-Up (days)
Subject death during Year 2 Follow-Up	Week 52	365
	Year 2 Follow-Up	Date of death – Treatment Start Date +1
	Year 3 Follow-Up	Date of death – Treatment Start Date +1
	Year 4 Follow-Up	Date of death – Treatment Start Date +1
	Year 5 Follow-Up	Date of death – Treatment Start Date +1
Subject death during Year 3 Follow-Up	Week 52	365
	Year 2 Follow-Up	730
	Year 3 Follow-Up	Date of death – Treatment Start Date +1
	Year 4 Follow-Up	Date of death – Treatment Start Date +1
	Year 5 Follow-Up	Date of death – Treatment Start Date +1
Subject death during Year 4 Follow-Up	Week 52	365
	Year 2 Follow-Up	730
	Year 3 Follow-Up	1095
	Year 4 Follow-Up	Date of death – Treatment Start Date +1
	Year 5 Follow-Up	Date of death – Treatment Start Date +1
Subject death during Year 5 Follow-Up	Week 52	365
	Year 2 Follow-Up	730
	Year 3 Follow-Up	1095
	Year 4 Follow-Up	1460
	Year 5 Follow-Up	Date of death – Treatment Start Date +1
Subject Last Known to be Alive during Year 2 Follow-Up	Week 52	365
	Year 2 Follow-Up	Last known alive date – Treatment Start Date +1
	Year 3 Follow-Up	Last known alive date – Treatment Start Date +1
	Year 4 Follow-Up	Last known alive date – Treatment Start Date +1
	Year 5 Follow-Up	Last known alive date – Treatment Start Date +1
Subject Last Known to be Alive during	Week 52	365
	Year 2 Follow-Up	730

Subjects Enter Follow-Up Period [1]	Subject Years Follow-Up Included By Year	Subjects Years Follow-Up (days)
Year 3 Follow-Up	Year 3 Follow-Up	Last known alive date – Treatment Start Date +1
	Year 4 Follow-Up	Last known alive date – Treatment Start Date +1
	Year 5 Follow-Up	Last known alive date – Treatment Start Date +1
Subject Last Known to be Alive during Year 4 Follow-Up	Week 52	365
	Year 2 Follow-Up	730
	Year 3 Follow-Up	1095
	Year 4 Follow-Up	Last known alive date – Treatment Start Date +1
	Year 5 Follow-Up	Last known alive date – Treatment Start Date +1
Subject Last Known to be Alive during Year 5 Follow-Up	Week 52	365
	Year 2 Follow-Up	730
	Year 3 Follow-Up	1095
	Year 4 Follow-Up	1460
	Year 5 Follow-Up	Last known alive date – Treatment Start Date +1

[1] Based on As-Treated Population Subsets for Years 2 to 5 Follow-Up.

Subjects Do Not Enter Follow-Up Period [1]	Subject Years Follow-Up Included By Year	Subjects Years Follow-Up (days)
Subject death during Week 52	Week 52	Date of death – Treatment Start Date +1
	Year 2 Follow-Up	Date of death – Treatment Start Date +1
	Year 3 Follow-Up	Date of death – Treatment Start Date +1
	Year 4 Follow-Up	Date of death – Treatment Start Date +1
	Year 5 Follow-Up	Date of death – Treatment Start Date +1
Subject Last Known to be Alive during Week 52	Week 52	Minimum (Last known alive date – Treatment Start Date +1, 365)
	Year 2 Follow-Up	Minimum (Last known alive date – Treatment Start Date +1, 365)
	Year 3 Follow-Up	Minimum (Last known alive date – Treatment Start Date +1, 365)
	Year 4 Follow-Up	Minimum (Last known alive date – Treatment Start Date +1, 365)
	Year 5 Follow-Up	Minimum (Last known alive date – Treatment Start Date +1, 365)

[1] Based on As-Treated Population Subsets for Years 2 to 5 Follow-Up.

